2.2 Secondary Objective

A sub-aim will examine whether the effect of incentives on participation intensity varies between the pro-social recruitment group and status-quo recruitment group.

3 INVESTIGATIONAL PLAN (brief overview)

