6 STATISTICAL CONSIDERATIONS

6.1 Statistical Methods

In Aim 1, we anticipate starting with a random selection of 600 providers from the list of eligible NC providers received from the NC Board of Medicine and NC Nursing Board, limiting to primary care providers identified as primary care through their provider type, which gives more than 90% power to detect a ten percentage point difference in the binary outcome, response to study recruitment. We will use binary models (logit, linear probability models) to examine response to recruitment as a function of study arm, controlling for provider type and county fixed effects.

For Aim 2, we will randomly recruit at least 60 enrollees (and up to 80 to enroll at least 20 providers per arm of this phase). The outcome to be monitored for Aim 2 is the number of ECHO sessions attended in the 6 months following randomization. Because this is a pilot study, the sample size is not powered for the primary outcome, number of ECHO clinics attended. We will conduct a negative binomial or other count data model (depending on statistical tests) of the number of sessions as a function of financial incentive arm to estimate the effect of financial incentives on participation.

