8 STUDY INTERVENTION ADMINISTRATION

Phase 1 recruitment letters are designed in a 2 (prosocial mention of need for primary care providers trained in opioid use disorder treatment vs. none) x 2 (mention of additional financial supports available for participation in training vs. none). This yields 4 study conditions for recruitment letters:

- 1) Letter including prosocial messages and additional mention of practice supports available for participation,
- 2) Letter including prosocial messages but no additional mention of financial support available for participation,
- 3) Letter including an additional mention of financial support available for participation but no prosocial messages, and
- 4) Recruitment as usual letter that does not include prosocial messages or an additional mention of financial support available for participation.

Phase 2 examines participation in the learning community by group. Participants will be randomly assigned to 1 of 3 groups. The investigators are not disclosing the Phase 2 conditions until the end of the study, as approved by UNC's institutional review board (IRB).

At the end of data collection, we will send a debriefing form to all participants to share the information that we withheld from them at the beginning of the study.

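### The Aim 2 count model lists incentive arm only; pre-specifying follow-up window, provider type and the two letter factors would cheaply protect precision in an unstratified comparison of about 20 per arm

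*Combined protocol and SAP*

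**What the plan says.** Section 6.1 (Statistical Methods), repeated in the synopsis, plans a negative binomial or other count model of the "number of sessions as a function of financial incentive arm to estimate the effect of financial incentives on participation". No covariate, offset or exposure term is listed. In the same section the Aim 1 model examines "response to recruitment as a function of study arm, controlling for provider type and county fixed effects".

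On size, section 6.1 asks for at least 60 enrollees, and up to 80, so that each of three arms has at least 20. It adds: "Because this is a pilot study, the sample size is not powered for the primary outcome, number of ECHO clinics attended".

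Section 3.1 (Randomization) assigns Phase 2 arms in order from one pre-set random list with equal chances. It mentions neither strata nor blocks.

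Three things are known at that moment:

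- **Letter.** Phase 1 has already randomised each practice to one cell of a 2 x 2 design (section 8). One factor is the prosocial message; the other is "mention of additional financial supports available for participation in training vs. none". Section 2.2 plans to examine "whether the effect of incentives on participation intensity varies between the pro-social recruitment group and status-quo recruitment group".
- **Provider type.** It comes from the licensing-board lists (section 11).
- **Enrolment date.** Sections 3.1, 3.3 and 4.1 and Appendix Table 1 give 6 months of follow-up, or 9 months to anyone not finished by 3/9/2020. Section 4.1 makes study enrolment depend on elapsed time alone, so the window follows from enrolment date.

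**The concern.** Aim 2 is about a tenth the size of the initial Aim 1 mailing (60 to 80 against 600) and so more exposed to chance imbalance, yet only Aim 1 has covariates. The protocol's own text suggests that the omitted factors may relate to attendance. The sub-aim treats recruitment group as relevant to it, provider type is already an Aim 1 covariate, and the extra three months are explained by fewer sessions and a difficult practice environment.

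The follow-up window is the strongest case. A count model with no period or exposure term treats a 6-month count and a 9-month count as the same kind of observation.

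At stake is the precision of an admittedly unpowered estimate that section 1 says will inform a full-scale trial. The model family is also left to statistical tests, so an unnamed covariate set would be a second choice open after the data are seen.

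**Working it through.** **1. The plan's own figure.** Three arms of at least 20 give 3 x 20 = 60, which matches section 6.1. Aim 2 has no power calculation to reproduce.

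**2. Is the window a baseline variable?** Completion takes six months from enrolment. Not having completed by 9 March 2020 therefore means having enrolled after about 9 September 2019. Leaving withdrawals aside, the window is fixed by a date that precedes Phase 2 assignment and cannot depend on arm, so it is a legitimate covariate.

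**3. Chance imbalance.** Inputs: 20 per arm, simple randomisation (inferred from the text's silence), and a binary factor held by 50% of enrollees (assumed). Let X1, X2, X3 be independent Binomial(20, 0.5) counts and R = max - min. By exact enumeration:

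- 20 points is 4 of 20: P(R >= 4) = 0.509
- 30 points is 6 of 20: P(R >= 6) = 0.188

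For a factor held by 25% the values are 40% and 11%. The figures also depend on arm size: with 26 per arm (78 in all), 20 points needs 6 of 26 and 30 points needs 8 of 26, and the probabilities at 50% prevalence fall to 28% and 9%.

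**4. Cost if nothing predicts attendance.** As a linear-model approximation, arm only leaves 60 - 3 = 57 residual degrees of freedom and four added terms leave 53. The ratio of standard errors is sqrt((1 - R2) x 57/53), where R2 is the share of residual variance explained. At R2 = 0 it is sqrt(57/53) = 1.037, or about 4% wider. Break-even is R2 = 4/57 = 7%.

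**5. Gain in a count model.** The documents give no mean, dispersion or covariate effects. Assumed: lowest-arm mean 6 sessions; dispersion 0.5 or 1.0; n = 60 or 78; rate ratio of highest to lowest arm 1 or 2; two-sided 0.05; 400 runs per scenario. The adjusted model adds three binary terms (one for letter, provider type, period), one fewer than the fix below. The table gives the change in the empirical SD of the log rate ratio over eight scenarios per row, with one example (n = 60, dispersion 0.5, arm rate ratio 2).

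| Covariate rate ratios | Change in SD | Example SD | Example rejection rate |
|---|---|---|---|
| 1, 1, 1 | +2% to +7% | 0.253 to 0.260 | 77.8% to 77.0% |
| 1.25, 1.25, 1.5 | -3% to +1% | 0.250 to 0.244 | 78.0% to 79.2% |
| 1.5, 1.5, 2 | -15% to -4% | 0.310 to 0.263 | 64.5% to 79.0% |

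The last example is the most favourable of its eight. With dispersion 1.0 the SD goes from 0.366 to 0.334 and rejection from 45.8% to 54.0%. Wald tests rejected in about 3% to 10% of null runs under either model, so the SD is the safer measure.

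**6. Window term alone.** The SD changed by about 0 to +1.5% with no period effect, -3% to -5% at a rate ratio of 1.5, and -6% to -7% at 2. These values move by a point or two between simulation runs.

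**7. Bias.** With a true log rate ratio of ln 2 = 0.693, the arm-only mean was 0.67 to 0.71. The arm-only estimate is essentially unbiased.

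**The case against.** The strongest reply is that nothing is broken. Phase 2 is randomised with equal chances, chance imbalance is ordinary sampling error that the standard error already reflects, and a sparse model is defensible in an unpowered pilot. A 20-point range in arms of 20 is only four providers. All of this stands. It limits the point to efficiency and pre-specification.

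Three further objections stand in part:

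- The absence of stratification is inferred. If the list were blocked, arms would be roughly balanced over calendar time and the figures in step 3 would not apply to the window. Adjustment could still remove variance that the window explains.
- Adjusted and unadjusted ratios target the same quantity only under a main-effects log-link model. The sub-aim asks whether the incentive effect varies by letter, and section 6.1 leaves room for other count models; for a zero-inflated or hurdle model the equality would not generally hold.
- Six against nine months is first an outcome-definition problem, which an indicator term does not settle.

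A reader might also draw stronger conclusions that the documents do not support:

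- *That the arm-only estimate is biased or confounded.* Randomisation and step 7 say otherwise.
- *That the letter is ignored in Aim 2.* The sub-aim uses recruitment group as a modifier, although no model is given for it. The letter is missing only from the stated main model.
- *That only half of those mailed learned of financial support.* Section 8 varies an additional mention, which does not show that the other letters were silent.
- *That Aim 1's "controlling for provider type and county fixed effects" obliges Aim 2 to match.* The two analyses may properly differ; the plan simply gives no reason.

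**Conclusion.** The point holds as a minor, low-cost improvement. The arm-only model is valid but leaves already-collected baseline information unused. It has no term for a follow-up window that differs between enrollees by a factor of 1.5 (9/6 months).

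The benefit is conditional: close to nil for moderate covariate effects, and a 4% to 15% smaller SD for strong ones, against about 4% wider intervals (2% to 7% in simulation) if none of the factors matters. These figures rest on an assumed mean, dispersion and covariate effects. The 51% and 19% rest on simple randomisation, exactly 20 per arm and a factor held by half of enrollees. The follow-up window has the best claim to inclusion; provider type and letter are reasonable additions.

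**What to change.** In section 6.1 and the synopsis, before outcome data are examined:

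1. Pre-specify the Aim 2 model as incentive arm plus follow-up window (6 versus 9 months, coded from enrolment date), with physician versus NP/PA, prosocial message (yes/no) and additional financial mention (yes/no) as the remaining main effects.
2. Report the arm-only ratio alongside. State that the two ratios share a target only under a main-effects log-link model, and keep the sub-aim's interaction separate.
3. Reconcile section 6.1's 6-month outcome with the 9-month window in section 3.1 and Appendix Table 1, since the meaning of the window term depends on it.
4. State whether the Phase 2 list was blocked or stratified.

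The cost is four model terms and a few sentences, with no new data and no change in sample size. The downside is the modest widening given above if none of the factors predicts attendance. With 60 to 80 enrollees the covariate set should not grow beyond this.

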7 STUDY INTERVENTION

See Table 2 in Appendix

8 STUDY INTERVENTION ADMINISTRATION

Phase 1 recruitment letters are designed in a 2 (prosocial mention of need for primary care providers trained in opioid use disorder treatment vs. none) x 2 (mention of additional financial supports available for participation in training vs. none). This yields 4 study conditions for recruitment letters:

- 1) Letter including prosocial messages and additional mention of practice supports available for participation,
- 2) Letter including prosocial messages but no additional mention of financial support available for participation,
- 3) Letter including an additional mention of financial support available for participation but no prosocial messages, and
- 4) Recruitment as usual letter that does not include prosocial messages or an additional mention of financial support available for participation.

Phase 2 examines participation in the learning community by group. Participants will be randomly assigned to 1 of 3 groups. The investigators are not disclosing the Phase 2 conditions until the end of the study, as approved by UNC's institutional review board (IRB).

At the end of data collection, we will send a debriefing form to all participants to share the information that we withheld from them at the beginning of the study.

9 SAFETY MANAGEMENT

There is no medical risk or risk of physical discomfort from this study. The risk to participants is minimal, and this does not meet the definition of a clinical trial, thus there is no data safety monitoring plan.

10 DATA COLLECTION AND MANAGEMENT

Procedures will be taken to minimize the possibility of a breach in confidentiality. No subjects will be identified in any publication or report of this study.

The nature of practice level data is ordinary, and unlikely to include socially stigmatizing conditions for providers. Secondary claims data will also be stored in secure databases. All working files are limited data sets, with patient names and contact information stripped off, but containing identified information on providers using a unique identifier (NPI) allowing linkage to data sources such as Medicaid prescribing information. This file will remain with the PI; the other research staff will access only files without patient names, addresses and other direct identifiers.

11 RECRUITMENT STRATEGY

PCPs will be identified from provider lists obtained through the NC Medical Board for physicians and physician assistants and the NC Board of Nursing for nurse practitioners. We will also use the DATA-2000 database of providers to help us identify PCPs who do not have waivers. Providers who are prescribing to Medicaid beneficiaries will be determined from NC Medicaid claims data, which is in use for the ECHO MAT study, and has been IRB approved for re-use for the ECHO Nudges study. We will use the list of providers currently participating in ECHO MAT, available to study investigators, to exclude the providers currently participating in ECHO (n=24). Once the denominator of eligible providers has been determined, the ECHO Nudges study team will randomly select providers in groups of 600 to randomize for pro-social or recruitment as usual invitations to participate in ECHO Nudges (and therefore ECHO MAT). From the group who decide to participate (outcome for Aim 1), we will re-randomize to one of the three arms of financial incentives. Effort to recruit providers for the Aim 2 analysis will follow immediately from the Aim 1 retention effort (e.g., providers must agree to participate in ECHO to be randomized to Aim 2). The number of sessions of participation within six months of engagement will be the Aim 2 outcome, thus no further efforts on retention will be utilized for the ECHO Nudges study.

12 CONSENT PROCESS

The project coordinator and/or the study team will give study information in both verbal and written form to each potential (provider) participant. Potential research participants are primary care providers in NC (MDs, DOs, NP, PAs). No patient identifying information will be collected through this effort. The consent form generated for enrolling PCPs by the investigators will be approved (along with the protocol) by UNC's IRB. Consent will be documented by the dated signature of the participant or the participant's legally authorized representative. The signature confirms that the consent is based on information that has been understood. Each participant's signed informed consent form will be kept on file by the investigators for possible inspection by regulatory authorities.

Since it is not possible to consent before recruitment to Aim 1, participants will complete the informed consent process at the beginning of Phase 2 of the study. The consent form will be shared with eligible participants when they contact the study team to enroll. Before enrolling in ECHO Nudges, participants will be asked to provide consent.

We will alter informed consent by only disclosing the study condition to which participants have been randomly assigned, and not the alternative Aim 2 treatment assignments, thus withholding the true purpose of the study, including the CT.gov #. This is because the aim of the second phase of the study is to test the hypothesis that compensating providers for time spent in MAT training increases the time they spend training. If we disclose that participants are randomly assigned to receive study incentives or not, and different amounts. That knowledge alone could lead to differential involvement in the study, which would make it impossible to test the hypothesis.

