
Nudges and Incentives to Enhance the Opioid Treatment Workforce

Study Objective(s)	Aim 1: To estimate the influence of informational nudges on the engagement of primary care providers in an opioid treatment learning collaborative to address the opioid overdose crisis. Aim 2: To estimate the influence of financial incentives on the participation intensity of primary care providers in an opioid treatment learning collaborative to address the opioid overdose crisis.
Study Design	The study is designed to be implemented in two phases. Phase 1 is the recruitment phase. Providers will be randomized to receive recruitment letters and emails from 1 of 4 conditions. Randomization for this phase will occur at the practice level, as determined by provider address. Participants that contact the study team and enroll in the study will begin Phase 2 of the study. In Phase 2 of the study participants will be randomly assigned to rewards for participation in ECHO MAT learning collaborative. Their participation in the learning collaborative will be tracked. Phase 2 of the study is a pilot.
Subject Population	Inclusion Criteria
key criteria for Inclusion and Exclusion:	
1. Licensed practicing Primary Care Provider (MD, DO, PA, NP)2. Currently practicing in NC, not currently participating in ECHO MAT Exclusion Criteria 
1. Another member of the same practice is already enrolled in the study (one provider per practice in Phase 2)2. Active participation in The University of North Carolina at Chapel Hill (UNC) ECHO Collaborative at beginning of study
Number of Subjects	Up to 80 to achieve at least 20 in each reimbursement arm
Study Duration	Each subject's participation will last six months with the exception of participants who had not completed as of 3/9/2020 whose participation was extended by 3 months due to decreased learning collaborative sessions resulting from COVID-19. The entire study is expected to last up to two years
Study Phases	(1) Recruitment : recruitment materials (letters or emails) sent once randomized to 1 of 4 conditions. Once participant enrolls, then
Screening	
Study Treatment	

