Follow-Up	(2) Randomization to 1 of 3 study arms: enrolled participants are re-randomized to 1 of 3 levels of reimbursement to estimate the influence of financial incentives in participation in learning collaboratives to address the opioid overdose crisis. Participation in learning collaboratives over 6 months will be

Nudges and Incentives to Enhance the Opioid Treatment Workforce

tracked. Participation in learning collaboratives will be tracked over 9 months for participants who did not complete as of 3/9/2020 due to the COVID-19 pandemic.

Safety Evaluations	The risk to participants is minimal.
Statistical and Analytic Plan	
In Aim 1, we anticipate starting with a random selection of 600 providers from the list of eligible NC providers generated from the NPI Registry, limiting to primary care providers identified through taxonomy codes, which gives more than 90% power to detect a ten percentage point difference in the binary outcome, response to study recruitment. We will use binary models (logit, linear probability models) to examine response to recruitment as a function of study arm, controlling for provider type and county fixed effects.
 
For Aim 2, we will randomly recruit up to 80 providers as needed to have at least 20 providers per arm enrollees for this phase of the pilot (20 providers per arm). The outcome to be monitored for Aim 2 is the number of ECHO sessions attended in the 6 months following randomization. Because this is a pilot study, the sample size is not powered for the primary outcome, number of ECHO clinics attended. We will conduct a negative binomial or other count data model (depending on statistical tests) of the number of sessions as a function of financial incentive arm to estimate the effect of financial incentives on participation.

DATA AND SAFETY MONITORING PLAN	The risk to participants is minimal, and this does not meet the definition of a clinical trial, thus there is no data safety monitoring plan.

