2.1 Primary Objective

Aim 1: To estimate the influence of informational nudges on the engagement of primary care providers in an opioid treatment learning collaborative to address the opioid overdose crisis. Primary care providers in North Carolina, including physicians, nurse practitioners, and physician assistants, will be randomly assigned to receive either a pro-social recruitment approach for participating in the UNC ECHO MAT intervention or standard recruitment practice. Treatment assignment will provide pro-social information, including customized figures on the opioid use epidemic in the provider's region and the

Nudges and Incentives to Enhance the Opioid Treatment Workforce

degree of the provider shortage in their region. The comparison arm will include a standard approach to recruitment that does not contain a pro-social recruitment message. Analysis of this data will provide estimates of the degree of responsiveness of providers to informational nudges.

Aim 2: To estimate the influence of financial incentives on the participation intensity of primary care providers in an opioid treatment learning collaborative to address the opioid overdose crisis. At the second stage, providers agreeing to enroll in the program will be re-randomized to one of three levels of reimbursement for time spent participating in the UNC ECHO MAT intervention. Analysis of this data will provide causal estimates of the degree of responsiveness of provider participation intensity to financial incentives.

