3.1 Study Design

In the first level of the study, providers will be randomized to receive one of two different recruitment letters. **The receipt of the letter is the intervention for Aim 1.** We will follow providers for up to 6 months after the mailing of the recruitment letters to monitor whether they attempted to sign up for the ECHO learning collaborative. This is the primary outcome for Aim 1.

Among the providers who contacted the study coordinator with interest in participating in the ECHO MAT learning collaborative (up to 80 of the providers), we will obtain consent to participate in the second level of the study, where providers will be **randomized to one of three levels of financial reimbursement for their time in the ECHO sessions. This is the intervention for the second level of the study.** We will monitor the number of sessions attended over 6 months from enrollment (9 months from enrollment for participants who did not complete as of 3/9/2020). This is the outcome for the second level of the study. We will send a letter to inform participants on how much they have participated and, if applicable, their incentive amount.

We may ask up to 44 of the study participants to participate in key informant interviews once their participation in the study has ended (6 months after enrollment). We will also contact a few individuals who initially indicated they were interested in participating, but then did not complete the consent process. We hope to learn why they did not complete the enrollment process.

We will contact study participants to notify them that we will look up their Waiver 2000 status (this is available through the DEA and publicly available on SAMHSA's website). We will not post or publish individual provider specific information on Waiver status.

Nudges and Incentives to Enhance the Opioid Treatment Workforce

We will use Medicaid claims data and ECHO learning collaborative participation data for the participants in our study to examine if the interventions in phase 1 or 2 have changed their MAT prescribing behavior, or their participation in ECHO MAT learning collaboratives.

Recruitment: Primary care providers will receive recruitment letters and may receive emails and phone calls based on the recruitment condition they are assigned to.

Randomization:

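### Section 12, read literally, shows the assigned Phase 2 payment condition before signature, while the rest of the plan puts consent or enrollment at or before the draw; if Section 12's order is followed, refusal can depend on arm and no record of it is described

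*Combined protocol and SAP*

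**What the plan says.** Section 12 (Consent Process) makes three statements that belong together:

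- On when the form is given: "The consent form will be shared with eligible participants when they contact the study team to enroll".
- On consent and enrollment: consent is sought first, and enrollment follows it.
- On what the consent process reveals: "We will alter informed consent by only disclosing the study condition to which participants have been randomly assigned". The other Aim 2 conditions are withheld.

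The same section indicates that the conditions differ in payment and that one may carry none: "participants are randomly assigned to receive study incentives or not, and different amounts".

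Other parts of the document give a different order. The Study Design row of the synopsis reads "Participants that contact the study team and enroll in the study will begin Phase 2 of the study", with random assignment to rewards coming next. The synopsis text on study phases says "enrolled participants are re-randomized to 1 of 3 levels of reimbursement". Section 3.1 says "we will obtain consent to participate in the second level of the study, where providers will be", and the sentence then describes the random draw of a payment level. The Phase 2 randomization paragraph of Section 3.1 assigns the next condition on a predetermined list at enrollment, and Section 3.2 randomizes after enrollment. Sections 1 and 2.1 re-randomize providers who agree to enroll. Section 11 re-randomizes those who have decided to take part and makes that agreement a condition of Aim 2 randomization.

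For Aim 2, Section 2.1 promises: "Analysis of this data will provide causal estimates of the degree of responsiveness of provider participation intensity to financial incentives".

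**The concern.** The order of signature and disclosure decides whether enrollment comes before or after randomization. If the condition is drawn and shown only after signature, the decision to enroll cannot depend on the arm. If it is shown first, a provider offered little or nothing can decline because of that offer. Enrollment then becomes a post-randomization event that the intervention itself can affect.

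Appendix Table 2 defines each Phase 2 group as providers who enroll and are assigned, so anyone who declines falls outside the comparison. If less motivated providers decline more often in the low-payment arms, those arms keep a more committed set of enrollees and the incentive effect is understated. The causal claim in Section 2.1 would then need qualification. Because this pilot is meant to inform a full-scale trial (Section 1), an unclear order could be carried into a study where selection bias would not shrink as the sample grew.

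**Working it through.** The plan gives no figure on this point to reproduce. Its one power statement concerns Aim 1, and Section 6.1 says Aim 2 is not powered. The check is therefore a comparison of the text, followed by an illustration on assumed inputs.

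**Step 1: order of events**

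| Place | Order described |
|---|---|
| Section 12 | form shared at contact; consent discloses a condition already assigned; then enrollment |
| Synopsis, Study Design | contact, enrollment, then assignment |
| Synopsis, study phases | enrolled participants are randomized |
| Sections 1 and 2.1 | agreement to enroll, then re-randomization |
| Section 3.1, design | consent to the second level, in which randomization takes place |
| Section 3.1, Phase 2 randomization | assignment on enrolling |
| Section 3.2 | enrolled, then randomized |
| Section 11 | decision to take part, then re-randomization |

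Only Section 12 describes how consent is conducted, and its natural reading differs from the others.

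**Step 2: are refusals recorded by arm?** Section 4.1 records reasons for withdrawal of subjects already in the study. Section 3.1 plans contact with a few people who did not complete consent, without a count or an arm. In Appendix Table 1, completed enrollment is compared by Phase 1 arm. No section describes recording refusals by Phase 2 arm, or says whether a provider who declines uses up a list position.

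**Step 3: possible size under Section 12's order.** Every input here is an assumption except the 20 per arm (Sections 3.3 and 6.1).

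- Expected attendance is gamma with mean m = 4, 8 or 12 sessions and shape k = 0.5, 1 or 2. Its Gini index G is 0.637, 0.5 or 0.375.
- A provider at attendance rank U (0 to 1) refuses with probability d × [1 + a × (1 − 2U)], where d is the arm's refusal rate and a is the strength of association with low attendance.
- Mean among enrollees = m × [1 + a × d × G/(1 − d)].
- Apparent paid/unpaid ratio at a true 1.00 = [1 + a·p·G/(1 − p)] / [1 + a·u·G/(1 − u)], with p and u the paid and unpaid refusal rates.

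Lower end (p = 10%, u = 40%, a = 1, k = 0.5): (1 + 0.1 × 0.637/0.9) / (1 + 0.4 × 0.637/0.6) = 1.071/1.424 = 0.752.

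Upper end (p = 5%, u = 20%, a = 0.5, k = 2): (1 + 0.5 × 0.05 × 0.375/0.95) / (1 + 0.5 × 0.2 × 0.375/0.8) = 1.0099/1.0469 = 0.965 (0.9647 before rounding).

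| Refusal, paid vs unpaid | a = 0 | a = 0.5 (k = 0.5, 1, 2) | a = 1 (k = 0.5, 1, 2) |
|---|---|---|---|
| 5% vs 20% | 1.00 | 0.942, 0.954, 0.965 | 0.892, 0.912, 0.932 |
| 10% vs 30% | 1.00 | 0.911, 0.928, 0.945 | 0.841, 0.869, 0.897 |
| 10% vs 40% | 1.00 | 0.854, 0.881, 0.907 | 0.752, 0.792, 0.833 |

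Equal refusal (p = u) also gives 1.00.

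**Step 4: against random error.** SE(log rate ratio) = √[2 × (1/m + 1/k)/20]. This runs from √[2 × (1/12 + 1/2)/20] = 0.242 to √[2 × (1/4 + 2)/20] = 0.474. Dividing the log shift by the SE for the same m and k gives 0.13 to 0.75 over the grid with a = 0.5 or 1. At m = 8, k = 1 (SE 0.335), a nominal 95% interval covers between 94.8% and 89.3%.

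**Step 5: cross-check.** Suppose refusal r occurs in the lowest-paid arm only, and refusers would have attended a fraction f of the overall mean. The apparent ratio is (1 − r)/(1 − r·f). For r = 10% to 40% this gives 0.95 to 0.75 at f = 0.5 and 1.00 at f = 1. In the limiting case f = 0, where every refuser would have attended nothing, it gives 0.90 to 0.60. At 0.60 the log shift (0.51) exceeds the largest SE above (0.474), so the statement that the shift is below one SE applies to the Step 3 grid and not to that limit.

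**The case against.** The strongest reply is that the intended order is fairly clear. Several sections, Section 11 most explicitly, put agreement or enrollment at or before the draw. Against them stands one sentence in Section 12 whose main subject is what is disclosed: the provider's own condition and not the alternatives. It can be read as disclosure after the draw and after signature. The consent form is not in the copy reviewed, and no section says the condition is printed on it before signature. This stands to the extent that the text shows an unreconciled contradiction, not that allocation came first. It does not remove the point, because Section 12 is where the conduct of consent is set out and it alters informed consent itself.

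Three stronger inferences are tempting, and the documents do not support them.

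- A reader might infer that refusals by arm would be lost for good. But Phase 2 uses a predetermined list. If refusals use up positions, entries consumed minus enrollees, by arm, would show them. What can be said is that no such record or reconciliation is described.
- A reader might infer that a log would establish the cause of unequal arms. With arms this small it might not; its value is transparent reporting.
- A reader might infer that signing first removes all arm-dependent loss. It removes arm-dependent refusal before enrollment. Section 4.1 still allows withdrawal for any reason afterwards, when the condition is known.

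It is also fair to say that Aim 2 is an unpowered pilot and that all the assumed shifts in the grid are smaller than its random error. That limits the likely harm to this study's estimate, but not the value of stating the order.

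**Conclusion.** The point holds in conditional form. Section 12 and the rest of the document give different orders for consent and the Phase 2 draw, and they must be reconciled. If signature comes first, refusal cannot depend on the Phase 2 arm and only the wording needs repair. If Section 12's literal order is followed, the enrollee-only comparison is protected only when refusal is equal across arms or unrelated to expected attendance, and an unqualified causal reading is not supported.

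The size cannot be determined from the documents, and zero is within the range. Under the assumed refusal rates, with half or full association with low attendance, a true ratio of 1.00 would appear as about 0.75 to 0.96, or 0.13 to 0.75 of one SE. The direction, toward understating the incentive effect, is itself an assumption about who refuses. The point should be fixed, with medium confidence that it affects conduct, because the intended order may already be the safe one.

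**What to change.** First establish which order is used, and make the synopsis and Sections 1, 2.1, 3.1, 3.2, 11 and 12 agree.

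- **If signature comes first:** amend Section 12 to say that the next list position is drawn, and the condition disclosed, only after signed consent. Cost: one clarifying sentence.
- **If the condition is shown before signature:** log the list position, arm, and consent or refusal of every provider shown a condition; state what happens to the list position of a provider who declines; report assignments and refusals by arm; and describe the enrollee-only comparison in Sections 2.1 and 6.1 as conditional on enrollment. Cost: a small tracking log and one or two sentences.

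Where disclosure now precedes signature, moving it to after signature would remove the problem at its source. It is an option rather than the required fix. Providers would sign without knowing their own payment condition, which withholds more than Section 12 now describes and needs IRB agreement.
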